4.3. Enrollment

Patient screening and enrollment

- The recruitment period will last from Jan to June 2024.
- Patients will be identified by the local research associate with support from responsible clinicians in each hospital, based on the eligibility criteria specified in Section 5.2.
- A trained research associate will then approach the patient (see Section 4.4 for details)
 - to explain the study objectives and approach based on the study information package (SIP, see ref) and a structured information session; this will include the expected benefits for the patients to contribute to the study and the expected workload during the assessment.
 - to discuss the Informed Consent Form (ICF see Annex 2) and check if the patient understands the form and is ready to sign it
 - to explain to the patient the need to sign a temporary collaboration agreement with the identified Health Data Intermediary (HDI) to pool non hospital data
 - to check if the patient is ready to evaluate the tool himself/herself.
- Following the information session, the patient who agrees to participate will be requested to
 - start to use personal apps (BrightFish¹⁴- see Section6), with a quality of life questionnaire, and explain why it is important and how to use the app
 - (for CVD patients) start using the provided medical device (Withings Blood Pressure Monitor, a CE marked device - see Section 6); training on how the device should be used will be provided
 - sign the ICF
 - \circ sign a collaboration agreement with the HDI collaborating with the hospital, for the duration of the study
- Once a patient has signed in for the evaluation study, the research associate will keep supporting him/her during the evaluation phase.

Expert curators enrollment

- Expert data curators are existing staff within the hospital that perform curation regularly; some of them contributed to the requirement of the AIDAVA prototype solution.
- Curators will be following the same information sessions and training given to the patients.

¹⁴ https://brightfish.com/solutions/ehealth/

4.4. Study execution : Study visits overview

4.4.1. Prerequisite (± 1 month before evaluation, respectively for G1 and G2)

Testing of data transfer (see more details in Section 11.4 on Data Protection)

- 1. Hospital data: Patient data (testing data) from hospital system to AIDAVA prototype (deployed in hospital) based on predefined data transfer specifications and signed data sharing agreement (see template in Annex 4 Data Transfer Specifications)
- 2. Personal Data to HDI: Data from Device/app API, and potentially GP data, to Health Data Intermediary based on agreed data sharing agreement, with patient consent
- 3. Personal Data to AIDAVA: Personal data gathered through HDI to AIDAVA prototype based on predefined data transfer specifications and signed data sharing agreement
- 4. Patient IPS to HDI: patient IPS (based on synthetic data) from AIDAVA prototype (deployed in hospital) to Health Data Intermediary, based on HL7 data format (with agreed version) and signed data sharing agreement

Pretraining of expert curators

- 1. Request to answer the health and digital literacy questionnaire to include in the user profile (in REDCap, User Profile Form)
- 2. Training on what the project is about, what AIDAVA is about, how to curate data and how to support the patient

Purchase of the medical devices in each site

4.4.2. First time patient (for G1 and G2)

This is applicable for new patients, for G1 (assessment period: July /Sept 2024) and G2 (assessment period: Feb/March 2026) of the prototype. See data collection and entry forms in Section 10 to collect the information on the patient visit

	CVD patients	BC patients
Screening and enrollment	Not applicable: CVD patients will be screened and enrolled after an infarction event (acute myocardial infarction - MI) W1,	Approximately up to 50 patients screened, 15 patients enrolled
(Checking I/E	D1 during the execution of the study starting August 2024	During regular hospital visit
criteria and		1. Checking I/E criteria (In REDcap, Patient Screening FORM)
participation to		2. Project introduction (10 min, doctor). Research associate
information		complete REDCap Form (in REDCap, Patient Screening FORM)
session)		If the patient meets the criteria and is interested in participating in the
G1 - Jan-June 2024		project, he/she will move on to the research associate

	CVD patients	BC patients
VISIT 0 - on site G2 - Sep 2025 - Feb 2026		 Under supervision of Research Associate - 30-60 min per patient Share details of the project with patients; Provision of SIP and explanation - including use of EQ-5D QALY quality of life questionnaire several time Introduction of HDI and questions regarding ownership and future use of the data through HDI Answer to questions Request to read and sign ICF and HDI agreement Research associate update REDCap Form (in REDCap, Patient Screening FORM) Confirmation of patient enrollment;
Site opening visit G1: June 2024 G2: Feb 2026	 Training of trainers (see training plan in Annex 3) : research asso a. Overall understanding on the AIDAVA project and tools b. Advanced training on the AIDAVA prototype (ingestion, c. How to support the patients d. Device and app installation for the patient: present devi 	ciate and expert curators will be trained for: curation, publishing) - for appropriate generation ce and show how it must be used
G1 and G2 VISIT 1 - on site W1 Day 1 (either elective outpatient clinic visit OR inpatient stay during index MI event),	 Approximately up to 50 inpatients screened, 15 inpatients enrolled (Note: Day1 and Day2 may seem busy for a patient recovering from MI; most patients are however recovering well and find difficult to remain in hospital during the monitoring period) 1. Checking I/E criteria (In REDcap) 2. Project introduction (10 min, doctor). Research associate complete REDCap Form (in REDCap, Patient Screening FORM) If the patient meets the criteria and is interested in participating in the project, he/she will move on to the research associate 3. Under supervision of Research Associate - 30-60 min per patient 	

	CVD patients	BC patients
	 a. Share details of the project with patients ; b. Provision of SIP and explanation - including use of EQ-5D QALY - quality of life questionnaire several time c. Introduction of HDI and questions regarding ownership and future use of the data through HDI d. Answer to questions e. Request to read and sign ICF and HDI agreement f. Provide medical device to patient 4. Research associate update REDCap Form (in REDCap, Patient Screening FORM) 5. Confirmation of patient enrollment; 	
	 Create HDI account (through AIDAVA) Questionnaire to specify user profile (In REDCap 3. Training session for the patient on the prototyp Patient fills EQ-5D form through HDI provided a Research associate complete REDCap Form (sources for enrolled patients Patient and expert curator curate medical data), User Profile FORM) e by the research associate pp in REDCap, Patient monitoring FORM) data extraction from different with AIDAVA
W1	CVD patient will use medical device	
Day 2 - 5	 Patient will use AIDAVA and test its functionalities, take notes and if necessary, will contact Helpdesk whenever needed Expert curator will curate the data in AIDAVA on demand. RA fill the patient monitoring form (in REDCap, Patient monitoring FORM) 	
W1 Day 5	 First calculation of SMART risk score by AIDAVA (automatically) and CVD expert (manually). Data collection and entry forms : Documentation of SMART risk score calculation result and time (in REDcap, Patient Monitoring FORM) by RA 	 System extracts the patient data for insertion into the local AIDAVA BC registry Queries identified as secondary end points will be fired automatically by the system and results available for display to the BC data users
	1. Data curators spreadsheet (Patient as curator and Exper Form)	t Curator), (in REDCap, Patient Curator FORM; Expert Data Curator

	CVD patients	BC patients
	 Data user/consumers spreadsheet (In REDCap Data use AIDAVA extract IPS and forward it automatically to the H monitoring FORM) 	r/consumer FORM) IDI + enter flag in Data collection and entry forms (REDCap, Patient
VISIT 2 - online W2 Day 1	CVD patients use medical device Check if there is any issue with the medical device (CVD patient only)	
	 Second training session on the prototype - online (open Patient and expert curator curate medical data using All RA fill the patient monitoring form (in REDCap, Patient in Complexity) 	questions) DAVA monitoring FORM)
W2 CVD patient will use medical device		
Day 2-5	 Patient will use AIDAVA and test its functionalities, take Expert curator will curate the data in AIDAVA on deman RA fill the patient monitoring form (in REDCap, Patient in AIDAVA) 	notes and if necessary, will contact helpdesk d. monitoring FORM)
VISIT 3 W2 Day 5	 Second calculation of SMART risk score by AIDAVA and CVD expert Data collection and entry forms: documentation of SMART risk score calculation result and time 	
	 AIDAVA extract IPS and forward it automatically to the HDI (+ enter flag in REDCap, Patient monitoring FORM) Patient and curator will fill in the system usability scale questionnaire online (in REDCap, System Usability Scale - SUS FORM) Data curators spreadsheet (Patient and Expert Curator). (in REDCap, Patient Curator FORM; Expert Data Curator Form) Data user/consumers spreadsheet (In REDCap Data user/consumer FORM) 	
W3		At the end of G1 - across all sites - fires the queries identified as secondary end points; RA reports the results in the data users/consumers spreadsheet (in REDCap Data user/consumer FORM).
End of evaluation	Delete personal patient data and PHKG (after finalisation of evaluation report), but keep evaluation score from G1.	
VISIT 4 - online W4	Feedback to patient	

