1.2. Schema

Figure 1. Schema of the assessment study

1.3. Schedule of Activities (SoA) - see more details in Section 4.

						Inte	rventi	ion Pe	riod V	Veeks (w	ith a wash	out of	16 to	18 mo	nths)					Notes
				Gener	ation	1				Rescreen										
Procedure	before W1)	W1 D1 V1	W1	W1 D5	W2 D1 V2	W2	W2 D5 V3	W3	W4 V4	Develop G2	(< 15 d before W1)	W1 D1 V1	W1	W1 D5	W2 D1 V2	W2	W2 D5 V3	W3	W4 V4	
Check I/E criteria (MD)	xBC	xCVD								(16 to 18	(x)	xCVD								REDCap Form 3
Intro to study (RA)	xBC	xCVD								months)	(x)									SIP (Annex 2)
Sign Informed consent	xBC	xCVD									(x)									On paper
Sign HDI agreement	xBC	xCVD									(x)									On paper
Create HDI account (through AIDAVA)	xBC	xCVD									(x)									
Data extract Hosp/HDI	xBC	xCVD																		After signing ICF
Training the research team	x																			Hospital contact persons, RA, expert curator, MD
Training - on site		x										x								
Training - on line					х										х					
User profile - Health and digital literacy		х										x								REDCap Form 1 (Patient, Curator)
Site monitoring forms		x	x	x	x	x	x	x	x			x	x	x	x	x	x			REDCap Forms 4,5,6,7 (RA)
System Usability Scale							x										x			REDCap Form 8 (Patient, Curator)
Fill in QALY		x										x								Personal Apps
Use BPM device		xCVD	xCVD		xCVD	xCVD				xCVD	xCVD	xCVD		xCVD	xCVD					See Section 6.2

		Intervention Period Weeks (with a washout of 16 to 18 months)															Notes			
	Screen				Gener	ation	1				Rescreen									
Procedure	before W1)	W1 D1 V1	W1	W1 D5	W2 D1 V2	W2	W2 D5 V3	W3	W4 V4	Develop G2	(< 15 d before W1)	W1 D1 V1	W1	W1 D5	W2 D1 V2	W2	W2 D5 V3	W3	W4 V4	
Curate data with AIDAVA		x	x	x	x	x	x					x	x	x	x	x	x			
Curator form - patient							x										x			REDCap Form 11 (Patient)
Curator form - expert	G0						x										x			REDCap Form 9, 10 (Curator)
IPS extract				x			x							x			х			
Extract BC registry				xBC			xBC							xBC			xBC			
Query Federated BC reg. /sec. endpoints				хBС				хBС						хBС				хBС		
SMART risk score (CVD)				xCVD			xCVD							xCVD			xCVD			Manual & auto
Data user form: BC, CVD							x										x			REDCap Form 12,13 (BC), and 14 (CVD)
Feedback to Patient (results + regular info)									x	every 3 mth									x	
Confirm delete data (if dropping out)									x										x	

Figure 2. Schedule of Activities

x = all patients

(x) = only for patients who did not participate to G1 evaluation

xBC = Breast Cancer patient only

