patients - across sites - receiving nodal radiotherapy out of any radiotherapy	P1 = Total number of patients 404684003 Clinical finding (finding) WITH 108290001 Radiotherapy (procedure)
	P2 = Total number of patients 404684003 Clinical finding (finding) WITH 168522007 Radiotherapy for lymphatic irradiation (procedure)

The actual metrics/ endpoints can then be defined as follows.

Objective	(Secondary) end point	
Metric 1. Time required to compute different queries of interest within the BC registry	Metric definition: Time to have an answer to the 3 queries (BC1, BC2 and BC3) with information from the BC registry - across sites Note 1: should include time of the BC specialist and supporting team (spending most of the time) Note2: should be the same between G1 and G2)	
	 Measurement: TBCx. User entry in dedicated "Data User form" (RedCap) for each of the queries 	
Metric 2: Accuracy of measurement	Metric definition: accuracy of the answer for each of the parameter between AIDAVA and the BC specialist	
	 Measurement: For each of the query (BC1, BC2, BC3), HBCx. Ask the value from the human (through RedCap Form) ABCx: get the value computed by AIDAVA ACCx: accuracy of calculation by AIDAVA (ABCx) compared to BC specialist (HBCx) 	

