4.4.4. Returning patients (for G2 only)

This is applicable only for patients who have participated to the assessment of G1 and are also assessing G2

	CVD patients	BC patients
2 weeks for start G2: Jan 2026	Refresh training of Expert curators and Research associates	
G2 VISIT 1 - on site W1 Day 1	 Upload of all data (starting from scratch) Patient will be called in for outpatient visit by the res Questionnaire to specify user profile (In Redcap, Use Training session for the patient on the prototype - G Patient fills EQ-5D QALY - quality of life questionnaire Research associate complete REDCap Form (in REDC Patient and expert curator curate medical data with 	search associate er Profile FORM) 2 version - by the research associate (2,5h) e through HDI provided app ap, Patient monitoring FORM) for enrolled patients AIDAVA
W1 Day 2-5	 CVD patient use the medical device Patient will use AIDAVA and test its functionalities, ta Expert Curator will curate the data in AIDAVA, on der RA fill the patient monitoring form (in REDCap, Patient) 	ake notes and if necessary, will contact helpdesk mand ent monitoring FORM)

	CVD patients	BC patients
W1 Day 5	 First calculation of SMART risk score by AIDAVA (automatically) and CVD expert (manually). Data collection and entry forms documentation of SMART risk score calculation result and time (in REDCap, Patient monitoring FORM) 	 System extracts the patient data for insertion into the local AIDAVA BC registry Queries identified as secondary end points will be fired automatically by the system and results available for display to the BC data users
	 AIDAVA extract IPS and forward it automatically to th Data curators spreadsheet (Patient as curator and E Form) Data user/consumers spreadsheet (In REDCap, Data 	ne HDI (+ enter flag in REDCap, Patient monitoring Form) Expert Curator). (in REDCap, Patient Curator FORM; Expert Data Curator user/consumer Form)
VISIT 2 - online W2 Day 1	CVD patients use medical device Check if there is any issue with the medical device (CVD patient only)	
	 Second training session on the prototype - online (open questions) Patient and expert curator curate medical data using AIDAVA RA fill the patient monitoring form (in REDCap, Patient monitoring Form) 	
W2	CVD patient use the medical device	

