9.1 Statistical Hypotheses

The primary objective is to demonstrate that G1 of the AIDAVA prototype is superior to the current situation in achieving data curation and publishing of personal health data; and that G2 is superior to G1. Improved efficiency will be measured through 4 endpoints i.e. M1 (usability of the tool), M2 (decreased time to curated data), M3 (high quality of resulting data), M4 (extraction of structured data from text).

- The 2 critical metrics are M2 (time) and M3 (quality).
- While important, **M1 (usability)** should be possible to improve (more training, increased explanation, ..) and the results of the evaluation will provide directions on how to improve.
- M4 (NLP performance) will improve with the introduction of new technologies (Large Language Models like ChatGPT and BARD) and is therefore less critical for the future of AIDAVA.

Thus, the null hypothesis to be tested in relation to the **primary estimand**¹⁷ is as follows.

• Null hypothesis (H0): The efficiency of data curation and publishing of personal health data is not different between G1 or G2 of the AIDAVA prototype and the current situation. There is no impact due to training on data curation.

vs.

- Alternative hypothesis (H1):
 - G1 of the AIDAVA prototype is more effective than the current situation with respect to the efficiency of data curation and publishing of personal health data and G2 is even more effective than G1.
 - The efficiency improvement is due mainly to the tool; some improvement is related to the training on data curation.

The null and alternative hypotheses corresponding to the secondary estimands are as follows:

Secondary objective for Breast Cancer Use Case:

- Null hypothesis: There is no difference with AIDAVA, to get an answer to specific queries on the BC registry across sites, in terms of accuracy and time.
- Alternative hypothesis (H2-BC): AIDAVA G1 provides correct answers on queries on the BC registries across sites (with an accuracy 90% or higher), while avoiding BC specialists (and supporting team) to spend time. G2 has similar or better results.

¹⁷ estimand (trial objective) is the target of estimation. In AIDAVA, the primary estimand is improved efficiency in data curation

Secondary objective for CVD specialists :

- Null hypothesis: There is no difference to compute SMART score for patients across sites, in terms of accuracy and time with AIDAVA.

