Training session for the patient on the prototype done?	 ⊕ ○ Yes ⇒ ○ No 			
Comments:	(free text)			
VISIT 1 (Week 1/Day 5) - Data extraction / calculation (the form	is filled by research associate)			
Date:	H Today Y-M-D			
Data curation (Week 1) by patient done?	 ⊢ ○ Yes ○ No 			
Data curation (Week 1) by expert curator done?	 ⊕ ○ Yes ⇒ ○ No 			
Did the patient check their International Patient Summary extract (transferred to HDI automatically)?	 ⊢ ○ Yes ○ No 			
Automatic extraction BC registry, query done (BC patients) an viewed by BC specialists?	d ⊕ ○Yes			
Comments:	(free text)			

For BC patients

VISIT 1 (Week 1/Day 5) - Data extraction / calculation (the form	m is filled by research associate)	
Date:	H Today Y-M-D	
Data curation (Week 1) by patient done?	 ⊢ O Yes ⊃ O No 	reset
Data curation (Week 1) by expert curator done?	 ⊕ O Yes ⇒ O No 	reset
How many times did you check your blood pressure with the BPM during the last week (expected to be a minimum of 3 times during the week, 3 times a day)?	(e.g. 2 or 3 how many times during the week) (e.g. frequency of each measurement)	
Did the patient check their International Patient Summary extract (transferred to HDI automatically)?	⊢ O Yes ⊖ O No	reset
SMART score (CVD patients) available and - viewed by CVD specialists - calculated by system	⊢ O Yes ⊖ O No	reset
Comments:	(free text)	

For CVD patients

Online training for patient (Week 2/Day 1)		
Date:	H Today Y-M-D	
Online training for patient done?	 ⊢ ○ Yes ⊃ No 	reset
Comments:	(free text)	

Online training for patient (Week 2/Day 1)					
Date:	H C Today Y-M-D				
Online training for patient done?	 (⊢) ○ Yes (○) No reset 				
Check any issue with medical devices (CVD patient only)	Issue:				
	(free text)				
	Proposal for resolution:				
	(free text)				
In case of change of medical device:	ID of old device:				
(CVD patient only)					
	Issue with old device:				
	(free text)				
	ID of new device:				
	Date of change: Today Y-M-D				
Comments:					
	(free text)				

For CVD patients

Visit 3 - Data extraction / calculation (Week 2/Day 5) (the form is filled by research associate)				
Date:	H Today Y-M-D			
Data curation (Week 2) by patient done?				
Data curation (Week 2) by expert curator done?				
Automatic extraction BC registry, query done (BC patients on and viewed by BC specialists?	ly) R ○ Yes			
Patient Curator form	Incomplete			
Expert Data Curator Form	Complete			
Data user/consumer (Breast Cancer Specialist) Form	Complete			

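### As scheduled, AIDAVA's answers to the breast cancer queries can reach the specialists before they give the reference answer, so ACCx is open to upward bias

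*Protocol*

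**What the plan says.** **The reference.** Section 3.2.1 (Metric 2) defines ACCx as AIDAVA's value for each of BC1 to BC3 set against the breast cancer specialist's value. The latter is obtained as follows: "HBCx. Ask the value from the human (through RedCap Form". No other reference is named. In Section 9.2, HBCx first appears at SDP1 (G1) and carries over to SDP2 (G2). SDP0 lists only effort and duration. Section 9.1 (H2-BC) expects correct answers "with an accuracy 90% or higher".

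**The display.** For first-time patients, Section 4.4.2 has the secondary-endpoint queries run automatically at Week 1 Day 5 with "results available for display to the BC data users". For returning patients in G2, Section 4.4.4 says they are "fired automatically by the system and results available for display to the BC data users". The list of definitions counts breast cancer specialists among the data users. In Section 10.3.2, the monitoring forms for Week 1 Day 5 and for Visit 3 carry a yes/no item on whether the query was done and "viewed by BC specialists".

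**The timing.** In the Schedule of Activities (Section 1.3), the row "Query Federated BC reg. /sec. endpoints" is marked at Week 1 Day 5 and Week 3. The row "Data user form: BC, CVD" is marked at Week 2 Day 5 only. Both hold for G1 and G2. The visit tables in Sections 4.4.2 and 4.4.4 list the data user form at Week 1 Day 5 and again at Visit 3. Section 4.4.2 adds a Week 3 run across all sites, which the research associate records in the data user form.

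**The concern.** An accuracy measure needs a reference produced without knowledge of the result under test. Here the reference is a person, and the schedule lets that person see the tool's answer before recording their own. A specialist who is unsure of a count, or who is pressed for time on a cross-site tally, may settle on or drift toward the displayed figure. Such drift shrinks the recorded disagreement and raises ACCx without AIDAVA being any more accurate. Because H2-BC carries an explicit mark, some of the apparent success could come from the order of events rather than from the tool. Analysis cannot restore independence afterwards, so the protection has to sit in the schedule and forms.

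**Working it through.** The protocol gives no figure to reproduce. The check is one of sequence.

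**Step 1. Place the events** (same pattern in G1 and G2 in the Schedule of Activities):

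| Event | Section 1.3 | Section 4.4 | Section 10.3.2 |
|---|---|---|---|
| Query run, results available | W1 D5, W3 | W1 D5 (4.4.2, 4.4.4); Visit 3 (4.4.4); W3 (4.4.2) | – |
| Viewing by specialists recorded | – | – | W1 D5, Visit 3 |
| Data user form | W2 D5 | W1 D5 and Visit 3 (W2 D5) | – |

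**Step 2. Read the order.** Under Section 1.3, the form follows the first availability of results by a week. Under Section 4.4, the first entry of the form falls on the same day as the display, and no order within the day is given. Neither reading makes HBCx precede availability.

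**Step 3. Look for a safeguard.** G0 supplies none: SDP0 has no HBCx, and the G0 breast cancer form in Section 10.3.4 asks only for times. No passage withholds results, locks HBCx, or assigns a reader who has not seen them. The cardiovascular arm at least has a senior physician who traces discrepancies back to their source (Section 3.2.2). The breast cancer arm has no such step.

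**Step 4. Illustrate how much drift would matter.** These values are assumptions, not estimates. Suppose accuracy is 100 minus the gap in percentage points between ABCx and an independent answer, a formula the protocol does not give. Let w be the share of that gap the specialist closes toward the display, and suppose the displayed and scored figures are the same. Then

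recorded gap = (1 − w) × true gap, and the recorded gap equals 10 points when w = 1 − 10 / true gap.

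| True accuracy | True gap | w at which 90% is recorded |
|---|---|---|
| 85% | 15 | 1 − 10/15 = 0.33 |
| 80% | 20 | 1 − 10/20 = 0.50 |
| 70% | 30 | 1 − 10/30 = 0.67 |
| 60% | 40 | 1 − 10/40 = 0.75 |

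Reading accuracy instead as a share of agreeing answers a, with a share w of AIDAVA's wrong answers adopted, gives a + w(1 − a) = 1 − (1 − w)(1 − a). This is the same algebra. The table shows only that partial drift can carry a near miss over the mark. It says nothing about the likely value of w.

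**The case against.** Several points on the other side are sound.

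- **The figure seen may not be the figure scored.** Each patient has an individual two-week window within July to September 2024, so at Week 1 Day 5 the registry may still be filling. The G1 run consolidated across sites comes in Week 3. A reader might infer that the specialist has already seen the exact value to be checked; the documents do not establish that. An interim value of the same percentage can still anchor, and viewing is also recorded at Visit 3, so the exposure is weakened rather than removed.
- **The wording is softer than a mandated showing.** Results are made available for display, and viewing is a yes/no item, not an instruction. It is nonetheless a tracked step.
- **The G1/G2 breast cancer form is named but not reproduced.** That HBCx is entered there is the natural reading, not a stated fact.
- **Bias is not certain.** BC1 to BC3 are counts from coded procedures and dates, which leave less room for judgement. A specialist who sees a discrepancy may recheck the records and correct a real human error, and agreement then rises because the reference improved. The recorded data could not tell this apart from anchoring, which is itself a reason to fix HBCx first.
- **The stakes are modest.** This is a secondary endpoint of a proof-of-concept study, and Section 3.2.1 claims no scientific meaning for the three queries beyond showing interoperability. The protocol still attaches a numerical mark to the result.

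**Conclusion.** The concern holds in a limited form. On either timing in the protocol, AIDAVA's query results are available to the specialists before, or on the same day as, the form that apparently collects the sole reference for ACCx, and nothing keeps that reference independent. ACCx, and any statement that the 90% mark was met, is therefore open to upward bias in both generations.

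A reader might go further and infer that ACCx is biased upward by a known amount, or that H2-BC would be met wrongly. The documents do not support that. They give neither an accuracy formula nor any measure of how far specialists would move, and they leave open that only an interim figure was seen. The conclusion rests on two readings: that HBCx is entered in the data user form, and that specialists do look at results made available to them. The point concerns the accuracy reference at G1 and G2, not the G0 time baseline.

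**What to change.** In Sections 1.3, 4.4.2 and 4.4.4 and in the monitoring forms of Section 10.3.2:

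1. In each generation, withhold AIDAVA's query results from the specialists who supply HBCx until they have entered and locked HBCx from their usual sources on the fixed patient list.
2. Release the display, and activate the viewing item, only after that lock.
3. Compare the locked HBCx with the Week 3 cross-site ABCx.
4. State which form collects HBCx, and reconcile its timing between the Schedule of Activities and Section 4.4.

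**Cost.** The sequence changes, but no new data are collected. Specialists would see results later, possibly not until the end of the generation, because the manual answer covers patients at all sites (45 in the G0 form) and individual patient windows are staggered. At G2, a specialist who saw the G1 results is not fully independent even with the lock, since returning patients' treatment history is largely the same. That should be stated as a limitation.
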